8.2.6 SERIOUS ADVERSE EVENT REPORTING

Serious events will be documented on the current OMB approved FDA Form 3500A following the current instructions for reporting. The study clinician will immediately report to the sponsor any serious adverse event, whether or not considered study intervention related, including those listed in the protocol or investigator brochure. The report must include an assessment of whether there is a reasonable possibility that the study intervention caused the event. Study endpoints that are serious adverse events (e.g., all-cause mortality) must be reported in accordance with the protocol unless there is evidence suggesting a causal relationship between the study intervention and the event (e.g., death from anaphylaxis).

All serious adverse events (SAEs) will be followed until satisfactory resolution or until the site investigator deems the event to be chronic or the participant is stable. Other supporting documentation of the event may be requested by the study sponsor and should be provided as soon as possible.

The medical monitor will review all adverse event reports and ensure that participants are receiving appropriate clinical care and identify any potential safety concerns. The medical monitor will assess the information provided to determine the relatedness of the event to the study intervention as well as propose any changes to the protocol and/or consent form based on the event. The study sponsor will be responsible for notifying the Food and Drug Administration (FDA) of any unexpected fatal or life-threatening suspected adverse reaction as soon as possible, but in no case later than 7 calendar days after the sponsor's initial receipt of the information. In addition, the sponsor must notify FDA and all participating investigators in an Investigational New Drug (IND) safety report of potential serious risks, from clinical trials or any other source, as soon as possible, but in no case later than 15 calendar days after the sponsor determines that the information qualifies for reporting.

8.2.7 REPORTING OF EVENTS TO PARTICIPANTS

Changes in the risk profile and/or risk/benefit ratio from observed adverse and/or serious adverse events will be communicated to participants through an IRB-approved revised consent form or addendum, as deemed appropriate given the information to be provided. If re-consent of the participants is required for continued participation, it must be obtained prior to continuing study related procedures.

8.2.7 REPORTING OF PREGNANCY

All females of reproductive potential should be instructed to contact the investigator immediately if they suspect they might be pregnant (e.g., missed or late menstrual period) at any time during study participation.

All investigators are required to report any pregnancy that occurs during the study within 24 hours of learning of the pregnancy. The site shall complete the Pregnancy Report Form and forward to the Sponsor's safety vendor Drug Safety Navigator (DSN).

The investigator is not obligated to actively seek pregnancy information in former study participants, but if the investigator learns of a pregnancy through spontaneous reporting, a Pregnancy Report Form must be completed and faxed to DSN.

9 STATISTICAL CONSIDERATIONS

9.1 STATISTICAL HYPOTHESES

The null hypothesis is that IFx-Hu2.0 may not be given safely as a neoadjuvant to patients with cutaneous squamous cell carcinoma, or basal cell carcinoma.

The alternative hypothesis is that IFx-Hu2.0 may be given safely as a neoadjuvant to patients with cutaneous squamous cell carcinoma, or basal cell carcinoma.

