1 PROTOCOL SUMMARY

1.1 SYNOPSIS

Title:	Phase 1 Trial of IFx-Hu2.0 to Evaluate Safety in Patients with Skin Cancer
Study Description:	One hundred patients will receive IFx-Hu2.0 on an outpatient basis at a single time point in a single lesion. These patients will be assessed for any immediate adverse reactions and at Week 4 (Day 28+-5 days) for any delayed adverse events.
Objectives:	
Primary Objective: To assess safety and feasibility
 
Secondary Objective: To assess post-therapeutic pathological response
 
Tertiary/Exploratory Objective: To assess anti-tumor immunity post-treatment.

Endpoints:	
Primary Endpoint: The primary endpoints of this trial will be the safety and feasibility of the treatment regimen. Safety will be reported using the most current version of the Common Terminology Criteria for Adverse Events (CTCAE). Feasibility will be defined as the ability to treat at least 85 of the approximate 100 patients enrolled without investigational product (IP) related dose-limiting toxicity (DLT).
 
Secondary Endpoints: The secondary endpoint is Pathological Response defined as a response assessment to IFx-Hu2.0 in tumor lesions excised by evaluating percent Residual Vial Tumor (%RVT), at four weeks as:
 
• pathological complete response (pCR),• major pathological response (mPR),• partial pathological response (pPR), or• pathological non-response (pNR) 
Tertiary/Exploratory Endpoints: Patient samples (plasma and/or serum) will be assayed to detect tumor antigen specific antibody generation in addition to a protein biomarker discovery assay specific to immuno-oncology therapy assessments. IHC will be performed on pre- and post-treatment tissue samples to contrast the cell sub-types across time points.

Study Population:	Adult male or female subjects with confirmed cutaneous squamous cell carcinoma, or basal cell carcinoma with lesions accessible for intralesional injection.
Phase:	Phase 1
Description of Sites/Facilities Enrolling Participants:	Approximately 5 NCI-designated cancer centers, academic medical centers, clinics, and doctor's offices within the United States, qualified to perform clinical studies under GCP.
Description of Study Intervention:	Plasmid DNA encoding a Streptococcal antigen in a cationic polymer-based solution in doses of 100 µg delivered intralesionally at a single time point "Week 0".
Study Duration:	12 Months
Participant Duration:	Up to six weeks

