3 OBJECTIVES AND ENDPOINTS

OBJECTIVES	ENDPOINTS
Primary	
Safety; i.e., to assess the safety, tolerability, and feasibility of treatment with IFx-Hu2.0 as a monotherapy in patients with skin cancer.
 
The primary endpoints of this trial will be the safety and feasibility of the treatment regimen. Safety will be reported using the most current version of Common Terminology Criteria for Adverse Events (CTCAE).
 
Feasibility will be defined as the ability to treat at least 80 of the approximately 100 patients enrolled without dose-limiting toxicity (DLT).

Secondary	
To assess post-therapeutic pathological response at four weeks post-treatment.
 
The secondary endpoint is Pathological Response defined as a response assessment to IFx-Hu2.0 in tumor lesions excised by evaluating percent Residual Vial Tumor (%RVT), at four weeks as:
 
• pathological complete response (pCR),• major pathological response (mPR),• partial pathological response (pPR), or• pathological non-response (pNR)
Tertiary/Exploratory	
To assess anti-tumor immunity post-treatment.
 
Patient samples (plasma and/or serum) will be assayed to detect tumor antigen specific antibody generation in addition to a protein biomarker discovery assay specific to immuno-oncology therapy assessments.
 
IHC will be performed on pre- and post-treatment tissue samples to contrast the cell sub-types across time points.

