9.4 STATISTICAL ANALYSES

9.4.1 GENERAL APPROACH

This is a safety and feasibility study that is designed to evaluate the safety and feasibility of IFx-Hu2.0 use as monotherapy. Safety will be assessed and reported based upon CTCAE v5.0 criteria. Feasibility will be defined as the ability to treat at least 80 of the 100 patients enrolled without dose-limiting toxicity.

The secondary endpoint is Pathological Response defined as a response assessment to IFx-Hu2.0 in tumor lesions excised at four weeks as; pathological complete response (pCR), major pathological response (mPR), partial pathological response (pPR), or pathological non-response (pNR) by evaluating percent Residual Vial Tumor (%RVT)(15).

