9.4.2 SAFETY ANALYSES

Maximum planned sample size	100
The event probability (ϑ)	0.2
Desired probability of early stopping	0.05

The trial will be stopped if the number of Dose Limiting Toxicities (DLTs) is equal to or exceeds b_n out of n patients with completed follow-up.

Number of Patients, n	1	2	3	4	5	6	7	8	9	10	11	12	13	14	15	16	17	18	19	20
Boundary, b_n	-	-	3	4	4	5	5	6	6	6	7	7	7	8	8	8	9	9	9	10
Number of Patients, n	21	22	23	24	25	26	27	28	29	30	31	32	33	34	35	36	37	38	39	40
Boundary, b_n	10	10	11	11	11	11	12	12	12	13	13	13	13	14	14	14	15	15	15	15
Number of Patients, n	41	42	43	44	45	46	47	48	49	50	51	52	53	54	55	56	57	58	59	60
Boundary, b_n	16	16	16	17	17	17	17	18	18	18	18	19	19	19	20	20	20	20	21	21
Number of Patients, n	61	62	63	64	65	66	67	68	69	70	71	72	73	74	75	76	77	78	79	80
Boundary, b_n	21	21	22	22	22	22	23	23	23	23	24	24	24	24	25	25	25	25	26	26
Number of Patients, n	81	82	83	84	85	86	87	88	89	90	91	92	93	94	95	96	97	98	99	100
Boundary, b_n	26	26	27	27	27	27	28	28	28	28	29	29	29	29	30	30	30	30	31	31

This boundary is equivalent to testing the null hypothesis, after each patient, that the event rate is equal to 0.2, using a one-sided level 0.008340 test.

Sequential boundaries will be used to monitor dose-limiting toxicity rate. The accrual will be halted if excessive numbers of DLTs are seen, that is, if the number of DLTs is equal to or exceeds b_n out of n patients with full follow-up. This is a Pocock-type stopping boundary that yields the probability of crossing the boundary at most [probability of early stopping] when the rate of DLTs is equal to the acceptable rate [event probability θ] (16).

θ	ϕ^*	$E[Y]$	$SD[Y]$	$E[N]$	$SD[N]$	$E[Y/N]$	$SD[Y/N]$
0.20	0.0497	19.31	4.40	96.58	16.21	0.21	0.10
0.30	0.6116	20.12	7.86	67.08	34.29	0.37	0.16
0.40	0.9883	11.85	6.31	29.65	22.10	0.50	0.18
0.50	1.0000	7.61	3.56	15.22	10.91	0.61	0.19
0.60	1.0000	5.71	2.31	9.52	6.29	0.71	0.19
0.70	1.0000	4.62	1.63	6.60	3.96	0.79	0.17
0.80	1.0000	3.89	1.14	4.86	2.51	0.87	0.14
0.90	1.0000	3.37	0.69	3.74	1.41	0.94	0.11
1.00	1.0000	3.00	0.00	3.00	0.00	1.00	0.00

Definitions:

Y = the number of events, random, between 0 and N

N = the number of patients, random, between 1 and K

ϕ^* = the actual probability of early stopping (hitting the boundary)

$E[]$ denotes the expected value (mean)

$SD[]$ denotes the standard deviation

Resource: <http://cancer.unc.edu/biostatistics/program/ivanova/ContinuosMonitoringForToxicity.aspx>

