2.2 Study Endpoints

2.2.1 Primary Endpoint

The primary endpoints of this trial will be the safety and feasibility of the treatment regimen. Safety will be reported using the most current version of the Common Terminology Criteria for Adverse Events (CTCAE).

Feasibility will be defined as the ability to treat at least 85 of the approximate 100 patients enrolled without investigational product (IP) related dose-limiting toxicity (DLT).

A DLT is defined as an adverse event equal to or greater than grade 3, at least possibly related to the investigational agent, occurring within a 4-week period following IP administration.

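### Protocol 9.1 states hypotheses with no DLT rate, level or decision rule, and no planned analysis tests them; the plan is one of estimation and should say so

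*Protocol*

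**What the plan says.** **Hypotheses.** Protocol 9.1 reads "The null hypothesis is that IFx-Hu2.0 may not be given safely as a neoadjuvant", and the alternative is the same sentence made positive. Neither gives a DLT rate, a level or a rule for deciding.

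**The one named test.** Protocol 9.4.2 describes its boundary as equivalent to "testing the null hypothesis, after each patient, that the event rate is equal to 0.2, using a one-sided level 0.008340 test". Accrual halts when DLTs reach the boundary. The crossing probability is controlled "when the rate of DLTs is equal to the acceptable rate", which is 0.2.

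**The primary threshold.** Protocol 3 has a primary objective "to assess the safety, tolerability, and feasibility of treatment with IFx-Hu2.0 as a monotherapy", and the DLT-free count sits under it. Protocol 9.4.1 states: "Feasibility will be defined as the ability to treat at least 80 of the 100 patients enrolled without dose-limiting toxicity". Protocol 3 also uses 80. The synopsis instead has "the ability to treat at least 85 of the approximate 100 patients enrolled", and SAP 2.2.1 agrees with the synopsis: "Feasibility will be defined as the ability to treat at least 85 of the approximate 100 patients enrolled".

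**Everything else is estimation.** Protocol 9.2 and SAP 2.3 justify 100 patients by the exact one-sided 95% upper limit on the DLT rate, with an example of 0.099 when no DLT is seen. SAP 3.2.1 reports the overall DLT rate with a 95% confidence interval and names no comparison rate.

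**SAP on testing and monitoring.** SAP 3.1 makes all tests two-sided at 0.05, SAP 3.6 plans no interim analysis, and SAP 3.8 records no change to the protocol's analysis. The available SAP text does not mention the boundary.

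**The concern.** A null of 'not safe' is rejected only by evidence that the DLT rate is low enough. That needs a rate to exclude, an error level and a rejection count, and 9.1 supplies none of them. The boundary cannot fill the gap because its null is that toxicity is acceptable. Failing to reject that null is not evidence for safety.

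A report that wished to conclude in favour of the 9.1 alternative would therefore have to lean on the DLT-free count. That count has no stated error rate, no passage ties it to 9.1, and its value depends on which section is read. At stake is whether the stated hypotheses can be accepted or rejected at all, and whether the primary threshold gives one answer.

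**Working it through.** **1. Reproduce the plan's boundary.** Inputs from Protocol 9.4.2: null rate 0.2, one-sided level 0.008340, n = 1 to 100. Rule: b_n is the smallest k with P(X ≥ k | n, 0.2) ≤ 0.008340. All 100 printed entries match, including b_100 = 31. Running the binomial process patient by patient and removing paths that reach b_n gives these crossing probabilities:

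| True DLT rate | Computed | Printed |
|---|---|---|
| 0.20 | 0.0490 | 0.0497 |
| 0.30 | 0.6137 | 0.6116 |
| 0.40 | 0.9878 | 0.9883 |

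The boundary is sound as a monitoring rule.

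**2. What not crossing shows.** P(cross) is 0.2389 at 25% and 0.6137 at 30%. P(not crossed) is then 1 − 0.2389 = 0.76 and 1 − 0.6137 = 0.39. At the final look 30 DLTs in 100 do not cross, and the exact one-sided 95% upper limit there is 38.4%.

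**3. What the count does.** At least 80 DLT-free of 100 means at most 20 DLTs; at least 85 means at most 15. 'Pass' below means that the boundary is never crossed and the count is met, with 100 treated. The last column is P(not crossed and 16 to 20 DLTs).

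| True DLT rate | Pass, 80 | Pass, 85 | Opposite conclusions |
|---|---|---|---|
| 5% | 0.9999 | 0.9998 | below 0.0001 |
| 10% | 0.998 | 0.959 | 0.04 |
| 15% | 0.928 | 0.567 | 0.36 |
| 20% | 0.554 | 0.128 | 0.43 |
| 25% | 0.147 | 0.011 | 0.14 |

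Against a rate of 0.20 neither cut-off is a 5% test: the chance of passing at that rate is 0.554 or 0.128.

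**4. Upper limits at the cut-offs.** The exact one-sided 95% limit is the 0.95 quantile of Beta(x + 1, n − x). With n = 100, x = 20 gives 27.7% and x = 15 gives 22.2%.

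**5. The precision example.** For x = 0 the limit is 1 − 0.05^(1/n). At n = 100 this is 0.0295, which rounds to 0.030. The printed 0.099 fits about 29 patients (0.0981 at n = 29, 0.1015 at n = 28).

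**6. The DLT definition.** Protocol 9.2 and SAP 2.3 require that the investigator and/or medical monitor judge the toxicity unacceptable. SAP 2.2.1 and 3.7 omit that condition. The rate to be estimated therefore has two definitions.

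**The case against.** The strongest reply is that a single-arm phase 1 safety trial is descriptive, so loose wording in 9.1 does no harm, and rewording it alone would change no table and no sample size. That is right as far as it goes, and it is why the remedy is to state estimation and not to add a test. The cut-off, the 0.099 and the DLT definition are errors in things the trial relies on, so they stand whatever is done with 9.1.

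A second reply is that the protocol does have a numeric notion of acceptable toxicity: 80 of 100 DLT-free is the same 20% that 9.4.2 calls acceptable. The match is real, but no section draws the link, and the synopsis and SAP use 85.

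Three stronger readings are tempting and are not supported:

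- *The plan treats an uncrossed boundary as proof of safety.* No section says so. The figures in step 2 describe a monitoring rule.
- *The choice of 80 or 85 decides the trial.* It matters only with 16 to 20 DLTs. At rates of 10% or less it seldom does. The earlier monotherapy trial, though with only six evaluable patients, reported no treatment-related event of grade 3 or above.
- *The SAP cancels the boundary.* Its section 2 presents itself as elaborating the protocol, and recording no change in 3.8 can mean that 9.4.2 stands. Toxicity monitoring need not count as an interim analysis, and the two-sided rule governs no test named in the available text. What is missing is a cross-reference.

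**Conclusion.** The concern holds. The 9.1 hypotheses cannot be formally accepted or rejected by anything planned, and the one named test points the other way. The trial remains interpretable as estimation of a DLT rate, so this should be corrected but does not undermine the design.

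The practical size lies mainly in the 80 versus 85 conflict: negligible at a 5% DLT rate, 0.04 at 10%, and 0.36 to 0.43 at 15% to 20%. The precision example overstates the upper limit more than threefold (0.099 against 0.030).

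The calculations assume exactly 100 treated patients, independent outcomes with a common DLT rate, and one DLT definition throughout. The true rates are assumed values, since the documents predict none. Statements about the SAP are limited to the text available for review.

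**What to change.** 1. **Protocol 9.1.** Replace the hypotheses with the estimation objective that 9.2 and SAP 3.2.1 already imply: the DLT rate in the safety analysis set with its exact one-sided 95% upper limit. State that neither meeting the count nor staying below the boundary is a test of safety. If the sponsor prefers to keep a test, it must state a null rate, a level and a rejection count. For scale only, an assumed null of 0.20 at one-sided 0.05 would reject with 13 or fewer DLTs in 100 (exact level 0.047, power 0.876 at a true 10%).
2. **Protocol 9.2 and SAP 2.3.** Change 0.099 to 0.030.
3. **Primary endpoint.** Reconcile 80 and 85 across the synopsis, Protocol 3 and 9.4.1, and SAP 2.2.1. Reconcile the DLT definition across Protocol 9.2 and SAP 2.2.1, 2.3 and 3.7. The sponsor chooses which applies. Express the cut-off as a proportion of those treated, or say how the count works if replacing treated withdrawals (Protocol 7.2) takes the number above 100.
4. **SAP 3.2.1.** Report the one-sided upper limit beside an exact two-sided 95% interval.
5. **SAP 3.1 and 3.6.** Cross-reference the 9.4.2 boundary as one-sided safety monitoring. This is a clarification.

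**Cost.** These are text edits, with no change to sample size, visits or boundary. The primary-endpoint edits need a sponsor decision and a protocol amendment. The trial also gives up a formal claim that safety was shown.

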9.2 SAMPLE SIZE DETERMINATION

The intent of this study is to enroll approximately 100 evaluable patients to assess the safety of IFx-Hu2.0 as a monotherapy. A sample size of 100 has the following precision for estimation of DLT rates ranging from 0.1 to 0.5. A DLT is defined as an adverse event equal to or greater than grade 3, at least possibly related to the investigational agent, occurring within a 4-week period following IP administration, and deemed as having unacceptable toxicity by the principal investigator and/or medical monitor. Precision is measured by 1-sided 95% upper confidence limit on the estimated DLT rate via exact binomial distribution. For example, if no DLT is observed in patients on IFX-Hu 2.0, then the true underlying DLT rate is lower than 0.099 with 95% confidence.

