2.2.2 Secondary Endpoints

The secondary endpoint is Pathological Response defined as a response assessment to IFx-Hu2.0 in tumor lesions excised by evaluating percent Residual Vial Tumor (%RVT), at four weeks as:

- Pathological complete response (pCR),
- Major pathological response (mPR),
- Partial pathological response (pPR), or

- Pathological non-response (pNR)

2.2.3 *Exploratory Endpoint*

Patient samples (plasma and/or serum) will be assayed to detect tumor antigen specific antibody generation in addition to a protein biomarker discovery assay specific to immuno-oncology therapy assessments.

IHC will be performed on pre- and post-treatment tissue samples to contrast the cell sub-types across time points.

2.3 *Sample Size*

The intent of this study is to enroll approximately 100 evaluable patients to assess the safety of IFx-Hu2.0 as a monotherapy. A sample size of 100 has the following precision for estimation of DLT rates ranging from 0.1 to 0.5. A DLT is defined as an adverse event equal to or greater than grade 3, at least possibly related to the investigational agent, occurring within a 4-week period following IP administration, and deemed as having unacceptable toxicity by the principal investigator and/or medical monitor. Precision is measured by 1-sided 95% upper confidence limit on the estimated DLT rate via exact binomial distribution. For example, if no DLT is observed in patients on IFX-Hu2.0, then the true underlying DLT rate is lower than 0.099 with 95% confidence.

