3. STATISTICAL METHODS

3.1 *General*

All data will be analyzed using the Statistical Analysis System (SAS®; Version 9.2 or higher). Continuous variables will be summarized using descriptive statistics, including sample size, mean, standard deviation (SD), median, minimum, and maximum. Categorical variables will be summarized using number and percent of subjects for each outcome.

All statistical tests will be two sided, and statistical significance level is 0.05.

3.2 *Subject Disposition, Demographics and Baseline Characters*

- Reasons for withdrawal will be summarized.
- Demographics and baseline characters will be summarized on safety analysis set using descriptive statistics.
- Medical history will be summarized with MedDRA system organ class (SOC) and preferred term (PT) for Safety analysis set.
- Prior and concomitant medications will be summarized with WHO Drug Class 3 name for Analysis of Study Endpoints

3.2.1 *Safety Analysis*

The safety analysis will be conducted on safety analysis set that includes all treated subjects.

Safety endpoints will be analyzed as summary statistics during treatment and/or as change scores from baselines such as shift tables. Treatment emergent adverse events (TEAEs) will be coded using Medical Dictionary for Regulatory Activities (MedDRA). TEAE severity and relationship to study treatment will be presented by dose cohort, MedDRA system organ class (SOC) and preferred term (PT).

The information reported about each AE will be the start date, stop date, severity, relationship, outcome, and duration). AEs leading to premature discontinuation from the study and serious treatment emergent AEs will be presented with either a summary table or a data listing.

- **Adverse Events**

TEAEs are defined as signs or symptoms that emerge during treatment or within 28 days of the last dose of Investigational Product, including those signs and symptoms that have been absent pre-treatment or that have worsened relative to the pre-treatment assessment. Any adverse event considered related to treatment will also be considered a TEAE, regardless of the elapsed time since the last dose of Investigational Product.

Number and percentage of subject with any DLT will be reported by dose cohort, MedDRA SOC and PT. Overall DLT rate for safety analysis set will be provided with 95%CI.

Number and percentage of subject with any TEAEs will be summarized by MedDRA SOC, PT, intensity, and relationship to the study treatment.

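### The zero-DLT precision example in Protocol 9.2 and SAP 2.3 gives an upper limit of 0.099; the stated method at n = 100 gives 0.0295

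*Protocol*

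**What the plan says.** Protocol 9.2 aims for about 100 evaluable patients and bases that number on precision; it gives no power calculation. It introduces the precision figures with "A sample size of 100 has the following precision for estimation of DLT rates ranging from 0.1 to 0.5" and defines the measure: "Precision is measured by 1-sided 95% upper confidence limit on the estimated DLT rate via exact binomial distribution". The example follows directly: "if no DLT is observed in patients on IFX-Hu 2.0, then the true underlying DLT rate is lower than 0.099 with 95% confidence".

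SAP 2.3 repeats the paragraph, with the same target ("The intent of this study is to enroll approximately 100 evaluable patients to assess the safety of IFx-Hu2.0 as a monotherapy"), the same measure and the same result: "if no DLT is observed in patients on IFX-Hu2.0, then the true underlying DLT rate is lower than 0.099 with 95% confidence".

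In the text available for review, 0.099 is the only precision value in either section. The values announced for DLT rates from 0.1 to 0.5 do not appear there. They may have been lost when the text was extracted from PDF, so their absence is not counted as an error.

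**The concern.** The zero-event case is easy to check, because the exact limit has a closed form and is close to 3/n. For 100 patients a reader expects about 0.03. A value near 0.10 looks wrong on sight, and it stands in both documents.

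Safety is the primary endpoint, and this sentence is the plan's only numerical statement of how precisely 100 patients would estimate the DLT rate. Someone judging the design from it would conclude that a trial with no DLTs could exclude only rates of about 10% or more. In fact it would exclude rates above about 3%. What is at stake is a correct description of the design for those who review it. No decision rule uses the number.

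**Working it through.** **Inputs** (Protocol 9.2, repeated in SAP 2.3)

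- Sample size: n = 100.
- Observed DLTs in the example: x = 0.
- Measure: exact binomial upper limit, one-sided, 95% confidence, so α = 0.05.
- Stated result: 0.099.

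**Step 1: the limit by the stated method.** With no events, the exact upper limit p solves (1 − p)^n = α, so p = 1 − α^(1/n).

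p = 1 − 0.05^(1/100) = 0.0295.

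The plan's figure is not reproduced. The ratio is 0.099 / 0.0295 ≈ 3.4.

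**Step 2: check by the tail probability.** At the true 95% limit, zero DLTs should have probability 0.05.

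- At p = 0.0295: (1 − 0.0295)^100 = 0.050.
- At p = 0.099: (1 − 0.099)^100 = 0.00003.

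**Step 3: other methods that might give 0.099, all with x = 0 and n = 100.**

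| Method | Upper limit |
|---|---|
| Exact, two-sided 95% | 0.0362 |
| Exact, one-sided 99% | 0.0450 |
| Exact, one-sided 99.5% | 0.0516 |
| Exact, one-sided at the monitoring level 0.00834 (Protocol 9.4.2) | 0.0467 |
| Wilson, one-sided / two-sided 95% | 0.0263 / 0.0370 |
| Jeffreys, one-sided 95% | 0.0190 |
| Uniform prior, one-sided 95% | 0.0292 |
| Rule of three, 3/n | 0.030 |

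None exceeds 0.052.

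**Step 4: other sample sizes, with x = 0 and the one-sided 95% exact limit.** The documents give no range for the approximate target, so 80 to 110 is an assumption.

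| n | 80 | 85 | 90 | 95 | 100 | 105 | 110 |
|---|---|---|---|---|---|---|---|
| Limit | 0.0368 | 0.0346 | 0.0327 | 0.0310 | 0.0295 | 0.0281 | 0.0269 |

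**Step 5: what 0.099 would require.** Solving for n with zero events gives n = ln(0.05) / ln(1 − 0.099) = 28.7. The limit is 0.1015 at n = 28 and 0.0981 at n = 29. Neither sample size section mentions a group of that size.

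Holding n = 100 instead, the one-sided limits are 0.0892 for 4 DLTs and 0.1023 for 5, so 0.099 falls between them. The two-sided 95% limit for 4 DLTs is 0.0993. These matches are numerical only; the documents do not show where 0.099 came from.

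**The case against.** The best defence is that the sentence is literally true. With no DLTs in 100 patients, a rate below 0.0295 is also below 0.099, so the claim is loose rather than false. The example sentence also names no denominator of its own; 100 comes from earlier in the paragraph. And nothing depends on the figure. The stopping boundary in Protocol 9.4.2 ("The trial will be stopped if the number of Dose Limiting Toxicities (DLTs) is equal to or exceeds") is built from a DLT rate of 0.2, and the reported interval ("Overall DLT rate for safety analysis set will be provided with 95%CI") will be computed from the data. The slip promises less precision than the trial would deliver.

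Much of this stands. The error is conservative, and it affects neither the sample size, the monitoring nor the analysis. It does not rescue the number. The sentence is offered as an example of a measure defined immediately before it, and 0.099 is not that measure's value. No other denominator appears in either section, so 100 is the only natural reading. Damage in PDF extraction is an unlikely explanation, because the same value stands in running prose in two separate documents.

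**Conclusion.** The figure is wrong as written. By the method that both documents state, the upper limit for no DLTs in 100 patients is 0.0295, not 0.099; the printed value is about 3.4 times too large. The conclusion uses only inputs given in the documents, and it survives every alternative method and sample size tried. Only the 80 to 110 range for the approximate target is assumed, and no value in it comes near 0.099.

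The consequence is limited to a planning statement, made in both documents, that understates the precision of the design. It does not show that 100 patients are too few, and it does not call the operating characteristics in Protocol 9.4.2 into question. Correction is worthwhile because this is the only precision result available in the sample size sections for the primary safety estimate.

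**What to change.** Replace 0.099 with 0.0295 (or 0.030) in Protocol 9.2 and SAP 2.3. The cost is one number in each document, with no change to conduct, sample size or decision rules.

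Optionally, confirm that the precision values announced for DLT rates 0.1 to 0.5 are present in the source documents. If they are not, the one-sided 95% exact limits at n = 100 are:

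| DLTs in 100 | 10 | 20 | 30 | 40 | 50 |
|---|---|---|---|---|---|
| Upper limit | 0.164 | 0.277 | 0.384 | 0.487 | 0.586 |

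Label them as fixed-sample limits that ignore continuous monitoring. The boundary in Protocol 9.4.2 is 31 DLTs at n = 100. If it is applied after each patient with completed follow-up, at most 30 DLTs can be seen at n = 100 without crossing, so the last two columns describe results that the trial would not reach at full size.
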